Increasing evidence shows that transcutaneous auricular nerve stimulation (taVNS) can significantly reduce multiple symptoms of stress disorder including depression, fatigue, cognitive impairment, anxiety, psychomotor retardation, sleep disturbance (Kong et al, 2018; Aranow et al 2020). One of the collaborators in this study [name] has developed and patented RAVANS, a type of taVNS, which synchronizes stimulation to the respiratory cycle, modulate vagal systems and optimize stimulations (Napadow et al 2012; Garcia et al, 2017; Yakunina et al 2017). RAVANS has been shown beneficial effect in pain management (Napadow et al 2012; Garcia et al, 2017).

In this study, we will conduct a randomized, double blinded, sham-controlled pilot study to **explore the effect of RAVANS on the symptoms in individuals diagnosed with PTLDS using psychometric measurement, function and cognitive test, and serum biomarkers.**

II. SPECIFIC AIMS

Aim 1. Determine if Respiratory-gated Auricular Vagal Afferent Nerve Stimulation (RAVANS) can improve symptoms of Post-Treatment Lyme Disease Syndrome (PTLDS)

Aim 2: Determine if RAVANS reduces inflammation as measured by serum biomarkers (IL6, IL-10, TNF, IL-1 β) after RAVANS treatment in people with PTLDS

Aim3: Determine if inflammation as measured by serum biomarkers (IL-6, IL-10, TNF, IL-1 β) correlates with severity of PTLDS.

INVESTIGATORS:

[name] [name], PhD, Spaulding Rehabilitation Hospital

Principal Investigator, recruitment, screening and consenting, data collection and analysis

[name], Spaulding Rehabilitation Hospital

*Medical Monitor

[name], Massachusetts General Hospital

Co-investigator, recruitment, data analysis

[name], LicAc, Massachusetts General Hospital

Co-investigator, RAVANS inventor, RAVANS technical support, data analysis,

*Responsibilities of the Medical Monitor

The medical monitor is required to review all unanticipated problems involving risk to subjects or others, serious adverse events and all subject deaths associated with the protocol and provide an unbiased written report of the event. At a minimum, the medical monitor must comment on the outcomes of the event or problem and in case of a serious adverse event or death, comment on the relationship to participation in the study. The medical monitor must also indicate whether he concurs with the details of the report provided by the principal investigator.

III. SUBJECT SELECTION

Inclusion criteria include:

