Subjects will receive RAVANS or sham treatment at clinic for 20 minutes. Subjects will complete the questionnaires (Horowitz Lyme-MSIDS, Sedentary Behaviors Questionnaire, Fatigue Symptom Inventory, Vulnerability Questionnaire, Brief Pain Inventory, Beck Depression Inventory, Beck Anxiety Inventory, Pittsburgh Sleep Quality Index), functional test (Timed Up and Go, 4 meter usually walking speed, NIH Toolbox cognitive battery), blood drawn for serum biomarkers (IL-6, IL-10, TNF, IL-1 β). Total visit times will be about 4 hours.

VI. BIOSTATISTICAL ANALYSIS

Our main outcome is to assess whether there is an improvement in symptoms (comparing before and after treatment) as indexed by HL-MSIDS score in the active RAVANS group as compared with sham. We chose the HL-MSIDS as the main outcome and therefore the other scale will be the secondary outcome. For the main analysis, we will compare the differences in HL-MSIDS changes between the two groups immediately after the end of treatment. We will therefore use an unpaired t-test for such analysis. Note here that we expect similar baseline level for both groups.

Besides this analysis, we will perform several exploratory analyses as listed below: we will compare the differences in changes in SBQ, FSI, BPI, BDI, BAI, PSQI, Timed- Up

and Go, 4m walk speed, NIHTB-CB, level of serum IL-6, IL-10, TNF, IL-1 β between the two groups immediately after the end of treatment. We will therefore use an unpaired t-test for such analysis.

Pearson correlation analysis will be applied to determine if serum level of biomarkers (IL-6, IL-10, TNF, IL-1 β) has correlation with symptom severity as index by HL-MSIDS, SBQ, FSI, BPI, BDI, BAI, PSQI, Timed- Up and Go, 4m walk speed, NIHTB-CB.

We will use the intention-to-treat analysis and do an analysis of only subjects that completed the 2-week study. For the intention-to-treat analysis, we will use a conservative method and assume that participants will not improve from the last measured point. The last-observation-carried-forward method will be appropriate because we expect no more than 10 percent of the observations were missing in each analysis.

Power analysis (e.g, sample size)

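### Aim 2 compares cytokine changes by t-test with no transformation or baseline adjustment; if values are right-skewed and effects proportional, a baseline-adjusted log analysis has clearly more power

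*Combined protocol and SAP*

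**What the plan says.** Section II gives the biomarkers two of the three specific aims: "Aim 2: Determine if RAVANS reduces inflammation as measured by serum biomarkers" and "Aim3: Determine if inflammation as measured by serum biomarkers" correlates with severity. Blood is drawn at Visits 1 and 6.

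Section VI introduces the secondary comparisons with "Besides this analysis, we will perform several exploratory analyses as listed below". The list includes changes in "level of serum IL-6, IL-10, TNF, IL-1 β between the two groups immediately after the end of treatment", followed by "We will therefore use an unpaired t-test for such analysis". For Aim 3, "Pearson correlation analysis will be applied to determine if serum level of biomarkers" correlate with HL-MSIDS and the other symptom, function and cognition measures.

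Section VI mentions no log transformation, rank-based method, normality check, adjustment for the Visit 1 level or rule for values below the assay limit, and none appears elsewhere. It does not use the word raw. Reading the analysis as one of untransformed concentrations is an inference from that silence, though the natural one.

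**The concern.** Concentrations are bounded below by zero and may be right-skewed, and a treatment that lowers them may well act in proportion to the starting level. If so, a few participants with high levels supply most of the variance of the raw change, and a t-test on raw changes loses power. A change score also gives up the precision that adjustment for the Visit 1 value would provide.

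With 24 per arm there is little power to spare, and these comparisons are the whole evidence for Aim 2. The risk is that a real reduction is missed. Choosing a transformation after seeing unblinded results would be open to challenge, so the choice should be made beforehand.

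**Working it through.** **Inputs from the documents.** Two arms; 24 per arm enrolled and 20 per arm before the dropout allowance (section VI, power analysis); cytokines at Visits 1 and 6; unpaired t-test on changes. The power analysis concerns the main outcome. The documents give no power, SD or effect size for any cytokine, so there is no stated figure to reproduce.

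**Assumptions, not in the documents.** Lognormal concentrations with log-SD s from 0.3 to 1.0; a true 40% reduction (30% in the mild-skew case); correlation 0.6 between log values at the two visits; no undetectable values; two-sided 5% tests.

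**Log-scale check by formula, s = 1.0, 24 per arm.**
- Effect on the log scale: ln(0.6) = −0.511.
- SD of the log change: s × √(2(1 − 0.6)) = 0.894. Standardized effect 0.511 / 0.894 = 0.57; noncentral-t power about 49%.
- SD after adjustment for baseline: s × √(1 − 0.6²) = 0.80. Standardized effect 0.511 / 0.80 = 0.64; power about 58%, before the small cost of estimating the slope.

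The raw change has no equally simple formula, so all three analyses were simulated. The log-scale results agree with the formulas.

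**Aim 2 power by simulation.**

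| Per arm | Log-SD | Reduction | Raw change | Log change | Log, baseline-adjusted |
|---|---|---|---|---|---|
| 24 | 0.3 | 30% | 97% | 99.5% | 99.8% |
| 24 | 0.5 | 40% | 85% | 97% | 99% |
| 24 | 0.8 | 40% | 39% | 67% | 76% |
| 24 | 1.0 | 40% | 24% | 49% | 57% |
| 20 | 1.0 | 40% | 19% | 42% | 49% |

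At log-SD 1.0 and 24 per arm, the log scale adds 49 − 24 = 25 points and baseline adjustment a further 57 − 49 = 8. These are two separate improvements.

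**Type I error.** With no effect, rejection is about 4 to 5% for the raw change and about 5% for both log analyses. The gain does not come from a looser test.

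**A different effect size.** With the effect fixed at 0.8 SD of the log change, 24 per arm and pre-post correlation 0.5 to 0.9, log-change power is about 77% throughout. Raw-change power is 71–73% at log-SD 0.25, 60–64% at 0.5 and 36–39% at 1.0.

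**Undetectable values.** With log-SD 1.0, a 40% reduction, and half of baseline values below the limit and set to half of it, power is 19/29/40%. The order is unchanged but the gain is smaller.

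**Aim 3, n = 48, r = 0.4 on the scale where severity is linear.** Power for raw Pearson / log Pearson / Spearman:

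| Log-SD | Severity linear in log concentration | Severity linear in raw concentration |
|---|---|---|
| 0.5 | 77 / 82 / 77% | 79 / 76 / 69% |
| 0.8 | 71 / 82 / 77% | 73 / 64 / 53% |
| 1.0 | 66 / 82 / 77% | 67 / 54 / 42% |

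The ranking reverses with the assumed relationship, and nothing in the documents favours either one. Raw Pearson's null rejection stays near 5%.

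**The case against.** The strongest reply is that the size of the loss rests on invented inputs. That stands. Log-SD, reduction and correlation are all assumed. The exclusion of acute illness, immunosuppressants and steroids (section III) may remove some sources of extreme values. With a 20% reduction at log-SD 1.0, power is 8/13/15%, so no method rescues Aim 2. If raw values are roughly normal with a coefficient of variation of 0.1 to 0.3, the log-change t-test ranges from a slight gain to a loss of about 4 points.

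The trial is also a pilot, and section VI labels the cytokine comparisons exploratory. This lowers the priority of the point but does not remove the gain.

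Three stronger readings are tempting and are not supported:

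- A reader might infer that high values make false-positive correlations likely. Under the skewed distributions examined, raw Pearson rejects a true null about 5% of the time.
- A reader might infer that Pearson should be replaced for Aim 3. The gain from logs or ranks exists only if severity is linear in log concentration; otherwise those methods lose power.
- A reader might infer that the log scale is free. It needs no extra participants, visits or blood, but it changes the quantity estimated to a ratio and needs a below-limit rule. The documents name no assay or limit, so the share of undetectable values is unknown.

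**Conclusion.** The point holds for Aim 2, conditionally. If cytokines are moderately to strongly right-skewed and effects are proportional, the planned raw-change t-test has about 39% power against 76% for a baseline-adjusted log analysis at log-SD 0.8, and 24% against 57% at 1.0. These figures assume a 40% reduction, correlation 0.6, 24 per arm and no undetectable values. At log-SD 0.5 the difference is 85% against 99%, and with mild skew little is lost. The documents cannot show which case applies.

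For Aim 3 no loss of power is established, because the better scale depends on an unknown relationship. There is no inflation of type I error under either aim. This is a modest improvement to exploratory analyses and does not touch the HL-MSIDS comparison.

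**What to change.** Before unblinding, amend section VI as follows.

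- **Aim 2:** analyse each log cytokine at Visit 6 by arm, adjusted for log cytokine at Visit 1, and report the ratio of geometric means (active/sham) with 95% CI.
- **Below-limit values:** state a rule in advance, for example half the assay limit, and report the number affected by arm and visit.
- **Aim 3:** keep Pearson as planned and add Pearson on log values or Spearman as a sensitivity analysis, reporting both.

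The cost is a few sentences, using samples already scheduled. Effects are read as ratios, and the gain shrinks if many values are undetectable.

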Respiratory-gated auricular vagus afferent nerve stimulation (RAVANS) will be performed with electrodes attached to the surface of the auricle. A small current will be delivered with a safe battery-powered portable stimulator, also used in other Partners IRB protocols (IRB#2016P000210). Current amplitude will be set between the sensitivity threshold and the pain threshold for each subject, to ensure non-noxious stimulation. Respiratory gating for stimulation will require real-time evaluation of the respiratory cycle, as described below.

For RAVANS setup, electrodes will be placed on the auricle of the left ear. Electrical stimulation to these electrodes will be provided by a current-constant stimulator (Cala

Health Inc, Burlingame, CA). Stimulation will be gated to the subject's own breathing, at a 1-second delay after peak inhalation (i.e. during exhalation.)

Sham stimulation: RAVANS device has a sham control mode on it. For sham stimulation, the device setup will be the same but no electrical current will be passed. Participant will be given instruction to use Mode 1(Active RAVANS) or Mode 2 (Sham stimulation) according to randomization. However, the participant would not know the setting of Mode 1 or Mode 2.

[figure not shown]

Figure 1: Setup of RAVANS: A. Electrode B. Placement of electrode on the auricle of the ear. C. Respiration belt and cables. D. Placement of respiration belt to gate the subject's breathing. E. Tablet to control the stimulation F. Cala stimulation program in the tablet

Assessments	Visit 1	Visits 2-5	Visit 6
DDQ	X		
FCI	X		
HL-MSIDS	X		X
SBQ	X		X
FSI	X		X

BPI	X		X
VQ	X		X
BDI	X		X
BAI	X		X
PSQI	X		X
Times Up and Go	X		X
4 meter Walk Speed	X		X
NIHTB-CB	X		X
Blood Drawn	X		X
RAVANS/ShamTreatment	X	X	X
Urine pregnancy test for women of child bearing potential	X		X
Approximate Time	4 hours	20 minutes per visit	4 hours

Visit 2-5:

Subjects will receive RAVANS or sham treatment at clinic for 20 minutes.

Visit 6:

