Sample size was determined with reference to other studies that used similar endpoints. We assume that a standardized difference of 0.8 (the difference between groups divided by the standard deviation) is conservative to detect a clinically meaningful difference between groups (active RAVANS and sham). We will assume a type I error of 5% (alpha), a type 2 error of 10% (beta) and therefore the power will be 90%. Using the sample size calculation for a normal distributed population (t-test), 20 participants per arm will be necessary (total of 40 participants). Conservatively, we expect a 20% rate of dropout or loss to follow-up. We will assume that dropout participants will not improve from the last measured point; thus the sample size will be increased by 20% to 48 participants (24 per arm).

VII. RISK AND DISCOMFORTS

Blood Draws. Blood drawing may cause a small amount of pain. In addition, participants may get a temporary bruise or “black and blue mark”. Rarely, people faint when their blood is drawn. Very rarely, the vein may become red and swollen, or infected. If this occurs, we will treat the problem. Blood drawn will be performed by clinical phlebotomists to minimize the risk and discomforts.

Surveys/ Questionnaires. Some of the questions in the questionnaires may seem personal or embarrassing. Participants will be instructed that they may refuse to answer any of the questions that they do not wish to answer. If the questions make a participant very upset, we will help them to find a counselor. If participants develop fatigue during completing the questionnaire, we all ask the participant to take break.

RAVANS Risks: There is a small possibility of slight and temporary discomfort at the site where the electrodes are placed. Potential vaso-vagal reactions to stimulation

resulting in dizziness or light-headedness. The participant will be instructed to sit in chair while receiving RAVANS/Sham treatment.

The RAVANS procedure is without significant safety concerns. The electrical stimulator, checked by MGH Biomedical Engineering, has a current limiter preventing harmful stimulation levels.

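### With HL-MSIDS measured only at Visits 1 and 6, LOCF sets the primary change to zero for anyone without a Visit 6 score, and its 10% justification is not reconciled with the planned 20% dropout

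*Combined protocol and SAP*

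**What the plan says.** Section VI makes HL-MSIDS the main outcome. By unpaired t-test, "we will compare the differences in HL-MSIDS changes between the two groups immediately after the end of treatment".

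The assessment table in section V marks HL-MSIDS at Visit 1 and Visit 6 and leaves Visits 2-5 blank. The text for Visits 2-5 describes treatment only: "Subjects will receive RAVANS or sham treatment at clinic for 20 minutes".

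On analysis sets, section VI says: "We will use the intention-to-treat analysis and do an analysis of only subjects that completed the 2-week study". It does not say which is primary. Intention-to-treat is listed first, and its no-improvement assumption reappears in the sample-size text, so it seems to be the intended primary.

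For missing outcomes, "we will use a conservative method and assume that participants will not improve from the last measured point". The only reason given for the method is numerical: "The last-observation-carried-forward method will be appropriate because we expect no more than 10 percent of the observations were missing in each analysis".

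The power paragraph uses another figure: "Conservatively, we expect a 20% rate of dropout or loss to follow-up". It continues: "We will assume that dropout participants will not improve from the last measured point; thus the sample size will be increased by 20"%, which gives 48 participants, 24 per arm. The standardised difference stays at 0.8 and the stated power at 90%.

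**The concern.** With one baseline and one post-baseline score, LOCF is baseline carried forward. The plan discloses that it assumes no improvement. It does not say that the last measured point is always Visit 1, so that every imputed change is exactly zero.

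Three things follow.

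- **Dilution.** Zeros in both arms pull the group difference towards zero, even when dropout is equal and random. The sample-size text adopts the same assumption but only adds participants. It does not reduce the effect to be detected.
- **Direction.** The method is called conservative, but this is not guaranteed. If both arms improve, zero imputation works against whichever arm loses more people. If that is sham, the bias favours active.
- **Justification.** The method is defended only up to 10% missing, while the trial plans for 20%.

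The plan also makes no provision for a participant who stops sessions but could still give a Visit 6 score, although section IV lets participants pause or leave at any time. Such a score would replace an imputed zero with a real value.

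**Working it through.** **Inputs from the documents:** standardised difference 0.8; type I error 5%; power 90%; 20 per arm before dropout and 24 after; dropout 20% (power paragraph); missing at most 10% (LOCF sentence).

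**Assumptions, not in the documents:** two-sided test; 0.8 scaled to the SD of change, set to 1; mean improvement in each arm; dropout by arm and its mechanism; correlation between baseline and Visit 6.

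**1. The plan's own figures.** The dropout step reproduces: 40 × 1.20 = 48. The base size does not. A two-sided t-test at 0.8 SD and 90% power needs 34 per arm, and 20 per arm gives 69%. That is a separate problem. It matters here only because the starting point at 24 per arm with no loss is 77%, not 90%.

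**2. The two rates.** 10% of 48 is 4.8 people and 20% is 9.6. If each participant had a 20% risk of dropout, the chance of at most 4 of 48 missing is 2.5%.

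**3. Dilution.** With a fraction m missing at random in each arm, the expected difference is 0.8 × (1 − m):
- m = 10%: 0.8 × 0.9 = 0.72 SD
- m = 20%: 0.8 × 0.8 = 0.64 SD

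The imputed zeros also change the spread. In an arm with mean improvement μ, the variance is (1 − m) + m(1 − m)μ². For m = 0.2, sham 0.5 and active 1.3:
- active: 0.8 + 0.16 × 1.69 = 1.070
- sham: 0.8 + 0.16 × 0.25 = 0.840
- SD from the average variance: √0.955 = 0.977
- effective difference: 0.64 / 0.977 = 0.655 SD, which gives about 60% power at 24 per arm

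**4. Power at a true effect of 0.8 SD, 24 per arm, equal random dropout.** LOCF is by simulation (1 million trials per cell). Observed changes only is by noncentral t averaged over binomial arm sizes.

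| Dropout | LOCF, sham +0 / +0.5 / +0.8 SD | Observed only | Cost of LOCF (points) |
|---|---|---|---|
| 0% | 77.4% | 77.4% | 0 |
| 10% | 72.0 / 69.0 / 66.5% | 72.6% | 1 / 4 / 6 |
| 20% | 65.8 / 60.3 / 55.7% | 67.1% | 1 / 7 / 11 |

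**5. Bias and false positives with no true effect.** If both arms improve by c, the bias towards active is c × (sham dropout − active dropout). At 10% active and 30% sham, c = 0.5 / 0.8 / 1.0 gives +0.10 / +0.16 / +0.20 SD. Reversing the dropout reverses the sign. Two-sided error with LOCF:

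| Dropout active / sham | c = 0.5 | c = 0.8 | c = 1.0 |
|---|---|---|---|
| 20% / 20% | 4.9% | 5.0% | 5.0% |
| 15% / 25% | 5.4% | 6.1% | 6.5% |
| 5% / 15% | 5.4% | 6.0% | 6.5% |
| 10% / 30% | 6.8% | 9.3% | 11.2% |

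**6. The replacement model.** This is a linear model of observed Visit 6 score on arm and baseline, with 20% random dropout and sham +0.5 SD. By simulation, power is 84% / 78% / 73% at correlation 0.3 / 0.5 / 0.7, against 60% for LOCF. About 7 points of the gain (60% to 67%) come from dropping LOCF, and the other 6 to 17 from baseline adjustment. These values depend on scaling 0.8 to the SD of change. If it is scaled to the Visit 6 SD, the effect after adjustment is 0.8 / √(1 − ρ²) = 0.84 / 0.92 / 1.12, and power is about 71% / 78% / 91%.

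**7. Limit of the replacement.** Suppose there is no true effect, 20% drop out per arm, active dropouts come only from below-average improvers, and sham dropout is random. If nobody is recovered, the model's bias is 0.13-0.17 SD (error 7.9-8.7%), against 0.16 SD for LOCF (9.1-9.6%). If half of the dropouts give a Visit 6 score, the model's bias falls to 0.06-0.08 SD. With three quarters it falls to 0.03-0.04 SD.

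**The case against.** The assumption is disclosed, and a completers-only analysis is already planned. With one post-baseline visit, that is close to a t-test on observed scores, so part of the fix only changes which analysis leads. This is fair. But the plan never says which one leads.

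The power paragraph labels its 20% as conservative, so 10% may be the expectation and 20% a margin. That reading is possible. A method that is kept should then be defensible at the margin, and its stated reason stops at 10%. Nor does it help to count both visits (9.6 missing of 96 scores is 10%), because the t-test analyses one change per person and 20% of those would be imputed.

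LOCF's own cost is modest. Most of the distance from 90% has other causes: the base sample size (90% to 77%) and loss of participants under any analysis (77% to 67%). The larger LOCF losses need an assumed sham improvement of 0.5-0.8 SD. The error rates of 7-11% need threefold unequal dropout, which nothing in the documents suggests over six sessions in two weeks. All of this stands, and those cells are illustrations only.

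Baseline adjustment is a separate improvement, and its gain should not be credited to dropping LOCF. That also stands, which is why an unadjusted alternative is offered below.

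**Conclusion.** The concern holds. For the primary outcome, LOCF means zero change for everyone without a Visit 6 score, and its only justification covers half the dropout for which the trial is sized. Under equal random dropout the effect falls from 0.80 to 0.64 SD at 20% (0.72 SD at 10%), and LOCF costs about 1 to 11 points of power (1 to 6 at 10%), depending on how much sham improves. The false-positive rate then stays near 5%, so the main harm is a diluted estimate and lost power.

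If dropout differs between arms and both improve, the comparison is biased in a direction that cannot be known in advance. The documents give neither dropout by arm nor expected improvement, so the likely size of that bias is unknown. For an exploratory pilot this should be corrected. It does not invalidate the design.

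**What to change.** 1. In section V, ask participants who stop sessions early, and who agree, to complete the Visit 6 HL-MSIDS anyway. Analyse them in the arm to which they were randomised.
2. In section VI, name one primary analysis: by randomised arm, a linear model of Visit 6 HL-MSIDS on arm and baseline HL-MSIDS, using all available Visit 6 scores and no LOCF. State that it is valid under missing-at-random and that, for those still missing, it is an available-case analysis. If the sponsor prefers the change-score t-test, apply it to observed Visit 6 scores without LOCF.
3. Keep zero change and completers-only as labelled sensitivity analyses. Do not call zero change conservative without condition. Report dropout by arm.
4. Delete the 10% justification and use the 20% planning figure throughout.

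The cost is SAP wording plus a small follow-up effort for one 55-item self-report questionnaire, not the full four-hour Visit 6. The downside is reliance on missing-at-random. If dropout follows outcome and nobody is recovered, the model is about as biased as LOCF, so step 1 matters most.

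### The stated 90% power is wrong: for a 0.8 SD difference, 20 per arm gives about 69% two-sided (80% one-sided), and 90% would need 34 (28) per arm

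*Combined protocol and SAP*

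**What the plan says.** Section VI (Biostatistical Analysis) names the HL-MSIDS score as the main outcome. Its change from before to after treatment is compared between active and sham by an unpaired t-test. No baseline adjustment is planned and the sidedness of the test is not given.

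The subsection on power sets out these inputs and results:

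- Effect size: "We assume that a standardized difference of 0.8 (the difference between groups divided by the standard deviation) is conservative". It refers to other studies with similar endpoints but does not give their results.
- Error rates: type I error 5%, and "a type 2 error of 10% (beta) and therefore the power will be 90" percent.
- Result: "Using the sample size calculation for a normal distributed population (t-test), 20 participants per arm will be necessary (total of 40 participants").
- Dropout: "Conservatively, we expect a 20% rate of dropout or loss to follow-up"; "thus the sample size will be increased by 20% to 48 participants (24 per arm").

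Two analyses are planned: "We will use the intention-to-treat analysis and do an analysis of only subjects that completed the 2-week study". For intention-to-treat, missing final scores are filled by carrying the last observation forward. The plan defends this on the ground that "we expect no more than 10 percent of the observations were missing in each analysis".

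**The concern.** Every input needed to check the sample size is in the paragraph except the sidedness, and the result does not follow from the inputs under either choice. A reader who meets a null result would think a true 0.8 SD effect had a 10% chance of being missed, when the chance is two to four times that. The plan also gives no power for the two analyses that will actually be run.

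Three smaller points sit in the same text:

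- Adding 20% to 40 does not leave 40 after a 20% loss.
- The expected missingness is 10% in one paragraph and 20% in the next.
- Calling 0.8 SD conservative is unsupported, because neither the reference effects nor a minimal important difference for HL-MSIDS is given.

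**Working it through.** **Inputs (Section VI).** Standardized difference d = 0.8; alpha = 0.05; target power 0.90; unpaired t-test; 1:1 allocation. Sidedness is not stated, so both readings are computed.

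**Trying to reproduce 20 per arm.** The normal approximation is n per arm = 2(z_alpha + z_beta)²/d².

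- Two-sided, 90%: 2(1.960 + 1.282)²/0.64 = 32.8, so 33. The exact t-test value is 33.83, so 34.
- One-sided, 90%: 2(1.645 + 1.282)²/0.64 = 26.8, so 27. The exact t-test value is 27.47, so 28.
- Two-sided, 80%: the exact t-test value is 25.52, so 26.
- One-sided, 80%: 2(1.645 + 0.842)²/0.64 = 19.3, so 20. The exact t-test value is 20.03.
- One-sample or paired formula, two-sided, 90%: 18.4, so 19. This does not match the plan's between-group effect size or its unpaired test.

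The nearest match to 20 is a one-sided test with 80% power, which contradicts the stated 90%.

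**Power at the planned sizes.** For the two-sample t-test the noncentrality is d√(n/2) with 2n − 2 degrees of freedom. At n = 20 it is 0.8 × √10 = 2.53, against critical values of 2.02 (two-sided) and 1.69 (one-sided).

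| Evaluable per arm | Two-sided | One-sided |
|---|---|---|
| 19 (completers, 20% dropout) | 67.0% | 78.1% |
| 20 (as stated) | 69.3% | 79.9% |
| 21.6 (completers, 10% missing) | 72.8% | 82.7% |
| 24 (no dropout) | 77.4% | 86.1% |

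The two-sided detectable difference at 90% / 80% power is 1.08 / 0.93 SD with 19 per arm and 1.05 / 0.91 SD with 20 per arm.

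**Dropout allowance.** 40 × 1.2 = 48, but 48 × 0.8 = 38.4, which is 1.6 short of 40. Keeping 40 after a 20% loss needs 40/0.8 = 50. The shortfall costs about 2 points of power (69.3% to 67.0%).

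**Intention-to-treat.** The assessment table in Section V scores HL-MSIDS only at visits 1 and 6. For visits 2–5 the text gives treatment alone: "Subjects will receive RAVANS or sham treatment at clinic for 20 minutes". Carrying the last observation forward therefore sets a dropout's change to zero.

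Assumptions not in the documents: SD of change 1 among those observed, the same dropout rate p in both arms unrelated to outcome, and a sham improvement of 0 to 0.8 SD. The mean difference becomes (1 − p) × 0.8. The variance in an arm with true mean change m becomes (1 − p) + p(1 − p)m².

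Worked case, p = 0.2:

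- Sham improvement 0: difference 0.64; variances 0.800 and 0.902; pooled SD 0.923; effective d = 0.694.
- Sham improvement 0.8 SD: difference 0.64; variances 0.902 and 1.210; pooled SD 1.028; effective d = 0.623.

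Put into the t-test formula with 24 per arm, these give about 65% and 56% two-sided. A simulation of 200,000 runs agrees within a point:

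| Sham improvement (SD) | 20% dropout, two-sided | 10% dropout, two-sided |
|---|---|---|
| 0 | 0.658 | 0.719 |
| 0.3 | 0.629 | 0.705 |
| 0.5 | 0.603 | 0.691 |
| 0.8 | 0.559 | 0.665 |

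One-sided, from 0 to 0.8 SD: 0.773 to 0.685 at 20% dropout and 0.821 to 0.776 at 10%.

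**The case against.** The core arithmetic cannot be defended, and nothing elsewhere in the plan recovers the lost power. The fair objections concern the points around it.

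- **It is a pilot.** A pilot need not have 90% power, and the plan describes its purpose as exploratory. That is a reason not to ask for more participants. It does not excuse the claim, because the plan names a main outcome, tests it between groups and states a 10% type II error.
- **The two missing-data rates may not conflict.** One counts observations and the other counts participants. With two HL-MSIDS scores each, 20% of 48 missing visit 6 is 9.6 of 96 scores, which is 10%. This reading is possible, so the point is a request for clarity rather than a proven contradiction. For a change score, the participant rate is the one that determines power.
- **The intention-to-treat range depends on assumptions from outside the plan.** This stands. At 20% dropout, a sham improvement of 1.2 SD would lower power to 49%, and a sham worsening of 0.4 SD would raise it to 68%. The range must be given with its assumptions.
- **Two-sided is a choice made for the sponsor.** The main outcome is worded as an improvement, and 20 per arm fits a one-sided test at 80% power, so the wrong entry may be the stated beta. The one-sided figures are given for that reason. They also miss 90%.
- **The dropout shortfall is immaterial and the reference studies cannot be seen.** Both are true, and both points are minor.

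**Conclusion.** The power statement is wrong as written. With the plan's own inputs, 20 per arm gives 69% power two-sided or 80% one-sided. Reaching 90% takes 34 or 28 per arm, which is 14 or 8 more per arm than stated. This result needs no outside assumption and holds under either sidedness, even with no dropout.

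For the planned analyses, two-sided, the type II error is about 33% for completers at 20% dropout. For intention-to-treat it is about 34–44% at 20% dropout or 28–34% at 10%, conditional on the sham, dropout and SD assumptions above. With 19 completers per arm, the difference detectable at 90% power is 1.08 SD, about a third larger than planned (1.08/0.8 = 1.35). The dropout arithmetic, the two missing-data rates and the unsupported effect size are secondary.

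**What to change.** Keep 48 participants and correct the text of Section VI.

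- Delete the 90% power and 10% beta claim, and the statement that 20 per arm is enough for it.
- State that the test is two-sided. If a one-sided test was intended, say so and give the one-sided figures.
- Give the power for 0.8 SD for each planned analysis. For completers (about 19 per arm) it is about 67%, with detectable differences of about 1.08 SD at 90% power and 0.93 SD at 80%. For intention-to-treat with dropouts set to no change (24 per arm) it is about 56–66% at 20% dropout and 66–72% at 10%, for an assumed sham improvement of 0.8 to 0 SD. Name these assumptions beside the figures.
- The 20-per-arm figure may stay for reference, with 69% power and detectable differences of 1.05 SD at 90% and 0.91 SD at 80%.
- Use one missing-data rate, expressed per participant, in the missing-data and power paragraphs, and give the power that goes with it. If 20% is kept, say that 48 enrolled leaves about 38 completers.
- Support the description of 0.8 SD as conservative from the reference studies, or delete it.

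The cost is wording in two paragraphs. Sample size, test and procedures do not change; the stated power becomes less favourable.
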